In addition, the following efficacy variables will be collected and summarized:

- PGIC
- Overall endometriosis-associated pain via NRS (7-day recall)
- Patient reported outcome (PRO) and Outcomes Rating Scales questionnaires

Safety:

BMD Assessments:

BMD assessments will be summarized. Modifiable and non-modifiable risk factors will be assessed as they relate to baseline BMD and changes in BMD over time, including: smoking and alcohol use, previous use of calcium and vitamin D, prior medications, race, age, height and weight (BMI), physical activity (collected via the International Physical Activity Questionnaire [August 2002] Short Last 7 days Self-Administered format) family history of fracture and family history of osteoporosis.

Other Safety Assessments:

Safety evaluations will include physical examinations, AEs and concomitant medications, clinical laboratory tests and vital sign measurements. Endometrial health will be assessed via TVU and biopsy.

Statistical Methods:

Efficacy:

The primary efficacy comparisons will be at Treatment Month 6 between the elagolix 200 mg BID plus E2/NETA treatment group (Group C) and elagolix 150 mg QD group (treatment Group B) in patients who are incomplete efficacy responders to elagolix 150 mg QD treatment at Month 3. Change and percent change from baseline in pain parameters collected via the e-Diary, proportion of responders for each pain parameter, change and percent change from baseline in protocol-specified rescue analgesic use, and other PROs will be summarized by month.

Statistical Methods (Continued):

Pharmacokinetic:

Plasma concentrations of elagolix and norethindrone will be listed for each subject by visit. Elagolix and norethindrone exposures will be summarized. Elagolix pharmacokinetic data may be combined with data from other studies to conduct population pharmacokinetic analysis and may be used in exposure-response analysis.

Pharmacodynamic:

Concentrations of estradiol will be obtained at designated visits throughout the study. Additional pharmacodynamic parameters may be calculated if useful in the interpretation of the data. Estradiol data may be combined with data from other studies and may be used for exposure-response analysis.

Safety:

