8.1.4.3 Secondary Efficacy Variables

Key Secondary Efficacy Endpoints

The following key secondary efficacy endpoints based on data collected during the first 6 months of the treatment period will be summarized by treatment regimen:

- Change from baseline in DYS
- Change from baseline in NMPP
- Change from baseline in dyspareunia
- Change from baseline in Daily Diary endometriosis-associated pain score via NRS
- Change from baseline in rescue analgesic use across both classes of rescue analgesics based on average pill counts
- Percentage of subjects with 30% or more reduction from baseline based on the 35 day mean of the Daily Diary endometriosis-associated pain score via NRS

Additional details regarding the key secondary efficacy endpoints will be provided in the SAP.

Additional Secondary Efficacy Endpoints

Additional secondary efficacy endpoints based on data collected during the first 6 months of the treatment period will include the following.

- Proportion of responders as assessed by change and percent change from Baseline in average pain score and rescue analgesic use monthly for DYS, NMPP, dyspareunia, and Daily Diary endometriosis-associated pain score via NRS, respectively.
- Proportion of responders as assessed by change and percent change from Baseline in average pain score alone (i.e., not taking into consideration of analgesic use) monthly for DYS, NMPP, dyspareunia, and Daily Diary endometriosis-associated pain score via NRS respectively.
- Change and percent change from Baseline, in the monthly average pain score (DYS, NMPP, dyspareunia), and Daily Diary endometriosis-associated pain score via NRS.
- Change from Baseline in rescue analgesic use (average pill counts) to treat endometriosis-related pain, as assessed using information from the e-Diary.
- Proportion of analgesic use responders monthly (based only on reduction of rescue analgesics used).

Additional secondary efficacy endpoints during the 24 months treatment period will include the following.

- Patient Global Impression of Change (PGIC).
- Monthly site administered overall endometriosis-associated pain questionnaire (7-day recall).
- Patient reported outcome (PRO) and outcomes Rating Scales questionnaires.

Summaries for Secondary Efficacy Variables

Unless otherwise specified, no statistical tests will be performed for secondary efficacy endpoints.

Analysis details will be specified in the SAP.

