8.1.4.3.2 Dyspareunia

The proportion of responders, mean change and percent change from baseline to each visit during the first 6 months of the Treatment Period in dyspareunia will be summarized similar to the method for DYS and NMPP.

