8.1.4.3.3 Rescue Analgesic Use for Endometriosis-Associated Pain

The use of rescue analgesics for endometriosis-associated pain will be reported by study subjects in the e-Diary during the first 6 months of the Treatment Period.

The rescue analgesic for endometriosis-associated pain taken by the subject will be summarized for the following analgesic categories: (a) NSAID or opioid, (b) opioid and (c) NSAID.

Baseline will be calculated as percentage of days of endometriosis rescue analgesic use for each analgesic category during the last 35 calendar days prior to and including Day 1 during the Screening Period. For the purposes of the rescue analgesic analysis, the number of pills within each class of rescue analgesic (NSAID or opioid) will be considered equivalent, regardless of specific pill choice, e.g., average NSAID pill count will consider all protocol specified NSAIDs specified in [Table 3](#) and will not be conducted separately by NSAID type.

The average pill count for each class of rescue analgesic for each visit during the first 6 months of the treatment period will be calculated by adding the daily pill count of the corresponding class of rescue analgesic in the analysis and dividing over the length of the window, generally equal to 35. For Month 1, average values will be based on data collected between Study Day 1 and the Month 1 reference study day. For Month 4, average values will be based on data collected between Month 3 reference study day and Month 4 reference study day.

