Appendix H. Analgesic Change During Treatment Period

Use of No Analgesics at Baseline		
Analgesic used during Screening	Analgesic dose status at end of study	Responder?*
None	None	Responder
	Opioid analgesic and/or NSAID is started	Nonresponder
Use of Only NSAID at Baseline		
Analgesic used at Baseline	Analgesic dose status at end of study	Responder?*
NSAID	Dose stopped, decreases, or is stable**	Responder
	Dose increases by 15% or more	Nonresponder
	Opioid analgesic is substituted or added	Nonresponder
Use of Only Opioid Analgesic at Baseline		
Analgesic used at Baseline	Analgesic dose status at end of study	Responder?*
Opioid analgesic	Dose stopped, decreases, or is stable**	Responder
	Dose stopped and NSAID substituted (any dose)	Responder
	Dose decreases and NSAID added (any dose)	Responder
	Dose stable** and NSAID added (any dose)	Nonresponder
	Dose increases by 15% or more	Nonresponder
Use of NSAID and Opioid Analgesic at Baseline		
Analgesics used at Baseline	Analgesic dose status at end of study	Responder?*
NSAID + opioid analgesic	NSAID dose stops + opioid analgesic use stops, decreases, or is stable**	Responder
	NSAID use stops + opioid analgesic dose increases by more than 15%	Nonresponder
	NSAID dose decreases + opioid analgesic use stops, decreases, or is stable**	Responder
	NSAID dose decreases + opioid analgesic dose increases by more than 15%	Nonresponder
	NSAID dose stable** + opioid analgesic use stops, decreases, or is stable**	Responder
	NSAID dose stable** + opioid analgesic dose increases by more than 15%	Nonresponder
	NSAID dose increases by more than 15% + opioid analgesic use stops	Responder

Use of NSAID and Opioid Analgesic at Baseline		
Analgesics used at Baseline	Analgesic dose status at end of study	Responder?*
NSAID + opioid analgesic (continued)	NSAID dose increases by more than 15% + opioid analgesic dose decreases	Responder
	NSAID dose increases by more than 15% + opioid analgesic dose is stable**	Nonresponder
	NSAID dose increases by more than 15% + opioid analgesic dose increases by 15% or more	Nonresponder

* Analgesic Responder = Defined as a subject who meets the criteria for no increase in analgesic use.

** Stable = Dose is the same as the baseline dose or increases by less than 15% of the baseline dose.

Assessment of dose is based on number of tablets of NSAIDS/opioids recorded in the Daily e-diary.

Document Approval

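### Percent change from baseline is planned for rescue analgesic use (in the synopsis only) and for dyspareunia, with no rule for a zero or near-zero baseline

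*Combined protocol and SAP*

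**What the plan says.** **Rescue analgesics.** The Statistical Methods part of the synopsis promises "change and percent change from baseline in protocol-specified rescue analgesic use", by month. Section 8.1.4.3 is narrower. Its key secondary endpoint is "Change from baseline in rescue analgesic use across both classes of rescue analgesics based on average pill counts", and the additional secondary endpoint for rescue use is likewise a change in average pill counts. Section 8.1.4.3.3 summarizes use in three categories ("a) NSAID or opioid, (b) opioid and (c) NSAID"). It defines the baseline as the percentage of days with use over the last 35 days before dosing, but defines use at each visit as an average daily pill count.

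**Zero baselines.** Appendix H opens with a block headed "Use of No Analgesics at Baseline". It then has separate blocks for women who used only NSAIDs and only opioids.

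**Dyspareunia.** The synopsis plans "Change and percent change from baseline in pain parameters collected via the e-Diary", and dyspareunia is one of the e-Diary parameters. Section 8.1.4.3.2 repeats this as "mean change and percent change from baseline to each visit during the first 6 months of the Treatment Period in dyspareunia". Section 8.1.4.3 adds monthly responder rates based on percent change.

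**Entry.** The pain minimums in Section 5.2.1 apply to DYS and NMPP only. None is set for rescue use or dyspareunia.

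**The concern.** A percent change divides by each woman's own baseline. At a baseline of zero it has no value; at a very small baseline it can be enormous. Both situations are expected here, and the available text gives no rule for either.

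Two things are at stake. First, a woman who starts a drug class from zero can only have increased her use of that class, and she is the one the percent-change column cannot show. The column therefore leans towards improvement by leaving her out. Second, a handful of women who took one or two tablets at baseline can swing the mean so far that a real fall looks like a rise. The two effects pull in opposite directions, so the reported figure cannot be read as a conservative or an optimistic one.

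There is also a plain mismatch: the synopsis announces a measure for rescue use that the statistical section does not list.

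**Working it through.** The plan states no figure on this point, so there is none to reproduce. The check is a comparison of the text, followed by arithmetic on assumed tablet counts, because the documents give none.

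**1. Can the baseline be zero?**

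| Variable | Zero possible? | Source |
|---|---|---|
| Any rescue analgesic | Yes | Appendix H, no-analgesic block |
| Opioids alone | Certain for NSAID-only users | Appendix H with 8.1.4.3.3 |
| NSAIDs alone | Certain for opioid-only users | Appendix H with 8.1.4.3.3 |
| Dyspareunia | Yes, if None scores 0 | Scale in 5.3.1.1; scoring inferred |
| DYS, NMPP | No | Entry minimums in 5.2.1 |

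The 0 to 3 scoring is stated in Section 8.1.4.2.1 for DYS and NMPP only. Because entry requires some DYS and NMPP, percent change is defined for both co-primary scales.

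**2. Arm size for the illustration.** From Section 8.3: 890 enrolled, 50% incomplete responders, 1:1 randomization. 890 × 0.50 / 2 = 222.5, taken as 222 (no loss before Month 3 assumed).

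**3. Zero baseline.** Percent change = 100 × (visit − baseline) / baseline, undefined at baseline 0. If 5%, 10%, 20% or 30% of 222 women had a zero baseline (assumed), 11, 22, 44 or 67 would have no value.

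Suppose all of these start at 0.5 pill/day while everyone else goes from 1.0 to 0.7:

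| Share starting from zero | Mean percent change where defined | Mean absolute change, all women | Ratio of group means |
|---|---|---|---|
| 5% | −30% | −0.26 | −27.4% |
| 10% | −30% | −0.22 | −24.4% |
| 20% | −30% | −0.14 | −17.5% |
| 30% | −30% | −0.06 | −8.6% |

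For the 10% row: 0.9 × (−0.3) + 0.1 × 0.5 = −0.22 pill/day. The ratio of means gives −0.22 / 0.9 = −24.4%. The percent-change column does not move at all.

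**4. Near-zero baseline.** One tablet in 35 days is 1/35 = 0.029 pill/day. A rise to 0.5 is 100 × (0.5 − 1/35) / (1/35) = +1650%. Let k of 222 women do this while the rest go from 1.0 to 0.7:

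| k | Mean percent change | Mean absolute change |
|---|---|---|
| 0 | −30% | −0.300 |
| 1 | −22% | −0.297 |
| 2 | −15% | −0.293 |
| 5 | +8% | −0.283 |
| 10 | +46% | −0.265 |

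For k = 5: (217 × (−30) + 5 × 1650) / 222 = 1740 / 222 = +7.8%. On the same data the ratio of group means is (217 × 0.7 + 5 × 0.5) / (217 × 1.0 + 5/35) = 154.4 / 217.14 = 0.711, a fall of 28.9%.

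**5. Baseline unit.** Section 8.1.4.3.3 has percentage of days at baseline and pills per day at follow-up. Neither an absolute change nor a ratio can be formed from these. The 15% rule in Section 8.1.4.2.1 already compares average pill counts with baseline, so a pill-count baseline is available from the Screening diary.

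**The case against.** The strongest reply is that little depends on this column. The same synopsis sentence plans absolute change, which keeps every woman with data. The co-primary responder rule in Appendix H deals with zero baselines explicitly. Section 8.1.4.3 also plans a monthly proportion of analgesic-use responders and states that, unless otherwise specified, secondary endpoints are not tested. All of this stands, and it limits the point to a descriptive summary.

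A second reply is that details are deferred to the SAP, which might use a median or set a zero-baseline rule. That is fair: the synopsis says only that rescue use will be summarized, not that a mean of individual percentages will be shown. A median would resist the near-zero baselines (in the k = 5 example it stays at −30%), but it would still leave out women with a zero baseline. No handling rule appears in the text available.

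Four stronger readings are tempting and not supported:

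- *That starters vanish from the analysis.* They are missing only from the percent-change column.
- *That everyone who starts a class is a Nonresponder.* Appendix H classes some opioid-only users who take up an NSAID as Responders, namely when the opioid is stopped or reduced.
- *That Groups B and C become incomparable.* They are randomized at Month 3 and baseline precedes Day 1, so their shares of zero and near-zero baselines agree in expectation. Group A is selected on response and is not comparable with them on any measure.
- *That the distortion has a known size.* The documents give no tablet counts, zero-baseline share or month-to-month variation.

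**Conclusion.** The point holds as a flaw in planned descriptive summaries. For rescue use, the synopsis names a measure that is undefined for women the plan itself foresees and whose mean is unstable at small baselines, and the statistical section does not list it. For dyspareunia the measure appears in both places, and the problem follows if None is scored 0, a natural reading of the scale but not one the text states.

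The direction and mechanism follow from arithmetic alone. The sizes, such as +8% from 5 of 222 women, are illustrations on assumed counts. The primary analysis, alpha, power and the expected balance between the randomized groups are unaffected. It is worth correcting because the correction is cheap and makes women who start a drug class visible.

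**What to change.** 1. **Synopsis, Statistical Methods:** delete subject-level percent change for rescue analgesic use, so that it agrees with Section 8.1.4.3, where there is nothing to delete for rescue use.
2. **Rescue summaries:** report absolute change in average daily pill count for all women; the ratio of group mean use (visit over baseline) for any rescue analgesic, NSAIDs and opioids; and the number of women starting each class from zero.
3. **Section 8.1.4.3.3:** define the rescue baseline as average pill count, the unit used at follow-up, instead of percentage of days. Step 2 depends on this.
4. **Dyspareunia (8.1.4.3 and 8.1.4.3.2):** state the scoring. Report absolute change for all assessable women. Limit percent change and percent-change responder rates to women with a baseline above 0, and show the number excluded.

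The cost is wording in the protocol and SAP; no new data are needed. The downside is the loss of a familiar percent figure for rescue use, which the ratio of group means replaces.

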1.2 List of Abbreviations and Definition of Terms

Abbreviations

Ab	Antibody
ABT	AbbVie
AE	Adverse Event
AESI	Adverse Event of Special Interest
ALT	Alanine Aminotransferase
AST	Aspartate Aminotransferase
BID	Twice daily
BMD	Bone Mineral Density
CIN	Cervical Intraepithelial Neoplasia
CR	Controlled release
CYP3A	Cytochrome P450 3A
DYS	Dysmenorrhea
DXA	Dual Energy X-Ray Absorptiometry
E2	Estradiol
E2/NETA	Estradiol/Norethindrone acetate
ECG	Electrocardiogram
eCRF	Electronic Case Report Form
EDC	Electronic Data Capture
e-Diary	Electronic Daily Diary
EHP-30	Endometriosis Health Profile-30
ePRO	Electronic Patient Reported Outcome
EQ-5D-5L	EuroQol-5D 5 Level
ER	Extended release
FSH	Follicle stimulating hormone
GCP	Good Clinical Practice
GnRH	Gonadotropin releasing hormone
HAV-IgM	Hepatitis A Virus immunoglobulin M
HBsAg	Hepatitis B Surface Antigen
HCV Ab	Hepatitis C Virus Antibody
HCRU	Health Care Resource Utilization
HDL	High-density lipoprotein

HIV	Human Immunodeficiency Virus
HIV Ab	Human Immunodeficiency Virus Antibody
HPV	Human Papillomavirus
HSIL	High-Grade Squamous Intraepithelial Lesion
ICH	International Conference on Harmonization
ICF	Informed consent form
IEC	Independent Ethics Committee
IPAQ	International Physical Activity Questionnaire
IR	Immediate release
IRB	Institutional Review Board
IUD	Intrauterine device
IRT	Interactive Response Technology
LDL	Low-density lipoprotein
NMPP	Non-menstrual pelvic pain
NRS	Numeric Rating Scale
NSAID	Non-steroidal anti-inflammatory drug
Pap	Papanicolaou
PD	Premature Discontinuation
PGIC	Patient Global Impression of Change
PK	Pharmacokinetic
PRO	Patient Reported Outcome
QD	Once a day
RBC	Red Blood Cell
SAE	Serious adverse event
SIS	Saline infusion sonography
TA MD	Therapeutic Area Medical Director
TSH	Thyroid Stimulating Hormone
TVU	Transvaginal Ultrasound
WPAI:SHP	Work Productivity and Activity Impairment Questionnaire – Specific Health Problem

Pharmacokinetic and Statistical Abbreviations

ANOVA	Analysis of variance
ANCOVA	Analysis of covariance
AUC	Area under the plasma concentration-time curve
LOCF	Last Observation Carried Forward
MMRM	Mixed-model with repeated measures
ROC	Receiver Operating Characteristics
SAP	Statistical Analysis Plan
T _{max}	Time to maximum observed plasma concentration

Definition of Terms

Open Label Period	Portion of the Treatment Period (from Day 1 through Treatment Period Month 3) wherein all subjects will dose with unblinded active study drug (150 mg Elagolix QD).

3.0 Introduction

3.1 Endometriosis

Endometriosis is defined as the presence of endometrial-like tissue outside the uterus.¹ Endometriosis primarily affects women of childbearing age, and is a frequently debilitating condition that is associated with a range of symptoms, the most common of which are dysmenorrhea (DYS) or painful menses, and non-menstrual pelvic pain (NMPP), as well as painful sexual intercourse or dyspareunia. Endometriosis is also a common reason cited for infertility.

The treatment of pain in women with endometriosis is remarkable for the number of therapeutic classes that are used to manage these symptoms and their use has been detailed in key clinical practice guidelines from the American College of Obstetricians and Gynecologists (ACOG),² American Society for Reproductive Medicine (ASRM),³ European Society of Human Reproduction and Embryology (ESHRE),⁴ the Society of Obstetrics and Gynecology Canada (SOGC) and the World Endometriosis Society (WES).⁵ To date, no therapy has an optimal benefit/risk profile, which attests to the unmet need for effective therapy for women suffering from endometriosis-associated pain.

3.2 Elagolix

Elagolix sodium (hereinafter "elagolix") is a novel, oral, short-acting, nonpeptide competitive gonadotropin releasing hormone (GnRH) antagonist that is being developed by AbbVie for the management of endometriosis with associated pain and heavy menstrual bleeding associated with uterine fibroids.

3.2.1 Preclinical Experience

3.2.1.1 Toxicology

A detailed discussion of the preclinical toxicology in addition to data on absorption, metabolism, distribution and elimination can be found in the Investigator Brochure.⁶

3.2.2 Clinical Experience

The current Investigator Brochure provides details of the pharmacology and pharmacokinetics of elagolix in humans, in addition to a summary of elagolix clinical studies in Phases 1, 2 and 3.⁶

In two replicate Phase 3 studies in women with endometriosis-associated pain, both elagolix treatment groups (elagolix 150 mg QD and 200 mg BID) met the coprimary efficacy endpoints showing a statistically significant higher proportion of responders for dysmenorrhea (DYS) and non-menstrual pelvic pain (NMPP) than those who received placebo at Month 3.⁷ Persistence of efficacy was observed through Month 6. The 150 mg QD dose demonstrated efficacy in 3 of 7 key ranked secondary outcome measures including significant reductions from baseline with the Daily Diary endometriosis-associated pain score via NRS (at Month 3), *DYS* (at Month 6) and *NMPP* (at Month 6). The 200 mg BID dose showed additional statistically significant improvement in all 7 key ranked secondary outcome measures, including reductions in any rescue analgesic agent (NSAIDs or opioids), and dyspareunia scores.

Consistent with estradiol (E2) suppression and previous elagolix studies, there was a dose dependent effect on BMD, such that a longer duration of treatment with the higher elagolix dose (200 mg BID) may require concomitant use of hormonal add back therapy to mitigate BMD loss.

Elagolix is not contraceptive and can change the menstrual bleeding pattern. A folliculogenesis study with elagolix revealed a dose-dependent suppression of ovulation. Elagolix should not be used in women who are pregnant or trying to become pregnant. Information regarding contraception counseling and pregnancy testing is provided in Section 5.2.4.

3.3 Differences Statement

This Phase 3b study will evaluate the safety and efficacy of elagolix 150 mg QD and elagolix 200 mg BID plus E2/NETA (1 mg/0.5 mg) QD in 18 to 49 year old

premenopausal women with endometriosis with moderate to severe pain. This study is intended to provide additional dosing guidance for elagolix 150 mg daily over a 2 year treatment period, and dose escalation to 200 mg BID with E2/NETA in incomplete responders. In addition, this study will investigate known modifiable risk factors for BMD decrease to further educate practitioners as to which patients may be at higher risks for BMD decrease. Such information would equip prescribers to safely prescribe elagolix for longer periods of time.

